# 14.3.6.4 Estimand strategy for time-to-event endpoints

The difference in the estimates of the cumulative incidence functions for the event of interest between delgocitinib cream 20 mg/g and cream vehicle will be evaluated at Weeks 2, 4, and 8.

### Primary estimand: 'while on treatment' strategy

With the 'while on treatment' strategy, response to treatment prior to the occurrence of the IEs is of interest. This strategy is chosen for the time-to-event endpoints with an expected early effect, e.g. reduction of HESD itch score (weekly average) of  $\geq 4$  points from baseline.

Let T represent the time from randomisation to the time-to-event endpoint and  $T_{\rm IE}$  represent the time from randomisation to occurrence of the first IE. The 'while on treatment' estimand evaluates:

$$Pr(T < T_{\rm IE} \land 16)$$

where  $T_{\rm IE} \wedge 16$  is the minimum of  $T_{\rm IE}$  and the end of the treatment period (administrative censoring time), corresponding to Week 16 in this trial. Since interest lies in estimating the time to achieving the endpoint while remaining on the randomised treatment, the occurrence of the IEs can be accounted for through the formulation of a competing risks model. It is assumed that IEs indicate failure of the randomised treatment.

## Primary analysis for the primary estimand

The null hypothesis,  $H_0$ :  $\lambda_{\text{delgo}}(t) = \lambda_{\text{vehicle}}(t)$ ,  $\forall t \in (0,16)$ , where  $\lambda(t)$  denotes the sub-distribution hazard rate associated with the time-to-event endpoint at time t (measured in weeks), will be tested against the alternative,  $H_a$ :  $\lambda_{\text{delgo}}(t) \neq \lambda_{\text{vehicle}}(t)$  based on Gray's test.

To quantify the magnitude of the potential treatment effect, the estimated cumulative incidence functions for the competing risks model will be presented for the treatment groups, based on the Aalen-Johansen estimator, along with 95% CIs.

Page 117 of 157

Cause-specific hazard Cox regression models will be fit for the cause-specific hazard for the 2 competing risks. The estimated cause-specific hazard ratios will be presented along with 95% CIs.

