#### 8.2 Inclusion criteria

The subjects must fulfil all of the following criteria to be eligible for the trial:

- 1. Signed and dated informed consent has been obtained prior to any protocol-related procedures.
- 2. Age 18 years or above at screening.
- 3. Diagnosis of CHE, defined as hand eczema that has persisted for more than 3 months or returned twice or more within the last 12 months.
- 4. Disease severity graded as moderate to severe at screening and baseline according to IGA-CHE (i.e. an IGA-CHE score of 3 or 4).
- 5. HESD itch score (weekly average) of ≥4 points at baseline. The baseline weekly average will be calculated from daily assessments of itch severity during the 7 days immediately preceding the baseline visit (Day -7 to Day -1). A minimum of 4 itch scores out of the 7 days is required to calculate the baseline average score.
- 6. Subjects who have a documented recent history of inadequate response to treatment with TCS (at any time within 1 year before the screening visit) or for whom TCS are documented to be otherwise medically inadvisable (e.g. due to important side effects or safety risks).
  - Inadequate response is defined as a history of failure to achieve and maintain a low disease activity state (comparable to an IGA-CHE score of ≤2) despite treatment with a daily regimen of TCS of class III-IV (potent to very potent) for EU and class IV-I (medium potency to very/ultra-high potency) for Canada, applied for at least 28 days or for the maximum duration recommended by the product prescribing information, whichever is shorter.

• Important side effects or safety risks are those that outweigh the potential treatment benefits and include intolerance to treatment, hypersensitivity reactions, and significant skin atrophy as assessed by the physician.

Page 48 of 157

- 7. Subjects adherent to standard non-medicated skin care including avoidance of known and relevant irritants and allergens.
- 8. A woman of childbearing potential\* must use an acceptable\*\* method of birth control throughout the trial up until the last application of IMP.

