## 9.3 Treatment assignment and blinding

## 9.3.1 Treatment assignment

Subjects who have been found to comply with all the inclusion criteria and not to violate any of the exclusion criteria will be randomised at baseline (Day 1) in a 2:1 ratio to receive treatment with either delgocitinib cream 20 mg/g or cream vehicle. The randomisation will be stratified by region (Europe or North America) and baseline IGA-CHE score (3 or 4).

The IRT system will be used to control randomisation and stratification factors, along with IMP supply chain and expiry tracking.

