# 12 Scientific rationale for trial design and appropriateness of assessments

## 12.1 Scientific rationale for trial design

This is a randomised, double-blind, vehicle-controlled, parallel-group, multi-site trial, which will be conducted in accordance with the protocol, ICH GCP, and applicable regulatory requirements. The trial will be conducted at multiple trial sites located in Europe and North America. High-quality trial sites with shared standards of practice will be selected.

Subjects with hand eczema represent a heterogeneous population as hand eczema is associated with different aetiologies, morphologies, and severities. To mitigate any potential difference in trial outcome based on baseline characteristics, the trial subjects will be randomised in a stratified manner. The randomisation will minimise selection bias and minimise influence of confounding factors, and the stratification will ensure a balance of the treatment groups with respect to baseline disease severity (IGA-CHE score 3 or 4) and region (Europe or North America). IGA-CHE severity is viewed as a strong prognostic factor while regional differences could occur given the heterogeneous population.

The vehicle control group will serve as reference and has been added to establish the efficacy and safety of delgocitinib cream in a blinded trial design. The randomisation ratio of 2:1 allows the majority of subjects to receive active treatment with delgocitinib cream 20 mg/g. Subjects who have intolerable CHE symptoms may receive rescue treatment if needed. Eligible subjects who complete the Week 16 visit (and who do not permanently discontinue IMP prior to Week 16) will be invited to continue in the LTE trial (conducted under a separate clinical trial protocol).

Topical application is considered the preferred route of administration for treatments for CHE, since CHE is a cutaneous disease characterised by few lesions affecting small areas of the skin. Topical administration will minimise the systemic exposure to the IMP and hence reduce the risk of AEs due to systemic exposure. Furthermore, a patient insights meeting supports that topical treatment for CHE is preferred over systemic treatment from a patient point of view.

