## 14 Statistical methods

## 14.1 Sample size

A total of 450 subjects will be randomised 2:1 to delgocitinib cream 20 mg/g or cream vehicle. The sample size is chosen to ensure that sufficient safety information including adequate long-term exposure data is collected.

With a one-sided significance level of 2.5%, a sample size of 450 subjects randomised will provide at least 99% power for detecting a treatment difference for the primary endpoint, assuming an IGA-CHE TS response rate at Week 16 of 40% vs. 10% for delgocitinib cream 20 mg/g and cream vehicle, respectively. The assumptions on response rates are based on results from the phase 2b dose-ranging trial (LP0133-1273).

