### Primary analysis for the primary estimand

Missing data for subjects who do not attend the visit for the endpoint of interest and do not experience an IE prior to this visit will be imputed as non-response.

The difference in response rates between the two treatment groups will be analysed using the CMH test stratified by region and baseline IGA-CHE score. The difference in response rates with 95% CI will be calculated by the Mantel-Haenszel method stratified by region and baseline IGA-CHE score.

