### First sensitivity analysis for the primary estimand

Missing data at the endpoint of interest, for subjects who do not experience the IEs prior to that, will be handled as follows. For subjects in the delgocitinib cream 20 mg/g group and the cream vehicle group, missing data will be imputed from a Bernoulli distribution with parameter p values 0.1 and 0.2. The same parameter p will be used for both treatment groups. The parameter values 0.1 and 0.2 are based on the response rates of IGA-CHE TS and HESD itch score (weekly average) ≥4 points, respectively, at Week 16 in the cream vehicle group in LP0133-1273 and will introduce uncertainty due to missing data. A MI procedure (100 iterations) will be used for each value of p. For each of the 100 complete datasets, the

Page 111 of 157

difference in response rates will be analysed using a CMH test stratified by region and baseline IGA-CHE score. The results of the analyses will be combined using Rubin's rule to provide the estimated treatment difference and associated standard error, and the 95% CI for the treatment difference will be calculated.

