### Primary analysis for the primary estimand

Missing data for subjects who do not attend the visit for the endpoint of interest and do not experience an IE prior to this visit will be imputed as WOCF (including the baseline value).

The change (or percentage change) from baseline to the endpoint of interest will be analysed using an ANCOVA model with effects of treatment group, region, baseline IGA-CHE score, and baseline value (endpoint of interest).

Page 114 of 157

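### No randomisation strata are named for the three exploratory time-to-event analyses; adding them is a small improvement at almost no cost

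*Combined protocol and SAP*

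**What the plan says.** Section 9.3.1 stratifies the randomisation by region (Europe, North America) and baseline IGA-CHE score (3, 4), which gives four cells. Section 12.1 gives the reason: "IGA-CHE severity is viewed as a strong prognostic factor", and regional differences are thought possible. It states no effect size and does not mention HESD.

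The analyses by endpoint type are:

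- **Binary (14.3.6.2):** "CMH test stratified by region and baseline IGA-CHE score". Through Sections 14.3.8 and 14.3.9 (Panels 24 and 25) this covers the 4-point reductions in HESD itch, HESD and HESD pain at fixed weeks.
- **Continuous (14.3.6.3):** ANCOVA with treatment, both stratification factors and the baseline value.
- **Time to event (14.3.6.4):** Gray's test, Aalen-Johansen curves by treatment group with differences at Weeks 2, 4 and 8, and "Cause-specific hazard Cox regression models will be fit for the cause-specific hazard for the 2 competing risks". No stratum or covariate is named.

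Section 14.3.9 refers the time-to-event endpoints back to 14.3.6.4. Section 14.3.14 adds only that Gray's test is two-sided at 5%.

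**The concern.** The same 4-point responses are analysed with the strata when they are counted at a visit and, as far as the text goes, without them when they are timed. No reason is given for the difference.

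Stratified randomisation balances the arms on the stratification factors. If a factor is prognostic, in either direction, an unstratified test still carries that between-stratum variation in its variance estimate, although the design has removed it from the treatment comparison. The test then becomes slightly conservative and loses some power. If the factor is not prognostic, stratifying should change almost nothing.

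Little is at stake. The three endpoints are exploratory and outside the closed testing procedure. An unadjusted hazard ratio is not biased; it estimates a marginal quantity and not a stratum-conditional one. Silence does leave both versions defensible once the data are unblinded.

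**Working it through.** **The plan's own figure.** The only stated power is for the primary endpoint (Section 14.1): at least 99% for 40% vs 10%, one-sided 2.5%, 300 vs 150 subjects.

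- Pooled rate: (300 × 0.40 + 150 × 0.10) / 450 = 0.30.
- SE under the null: √[0.30 × 0.70 × (1/300 + 1/150)] = 0.0458.
- SE under the alternative: √[0.40 × 0.60/300 + 0.10 × 0.90/150] = 0.0374.
- z = (0.30 − 1.96 × 0.0458) / 0.0374 = 5.6, so power exceeds 99.99%. The figure reproduces.

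No power or event count is stated for the time-to-event endpoints.

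**Inputs from the protocol.**

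- "A total of 450 subjects will be randomised 2:1 to delgocitinib cream 20 mg/g or cream vehicle" (14.1); two-sided 5% for Gray's test (14.3.14); follow-up ends at Week 16 (14.3.6.4).
- Itch is analysed in all subjects because criterion 5 of Section 8.2 requires "HESD itch score (weekly average) of ≥4 points at baseline". The HESD and pain endpoints use subsets.
- Phase 2b vehicle HESD itch response at Week 16 of about 0.2 (14.3.6.2, first sensitivity analysis). This is a point-in-time rate for itch only; cumulative incidence may be higher.

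**Test statistic.** With administrative censoring only, Gray's test is a log-rank test in which subjects with an intercurrent event stay at risk to Week 16. With D events (D₁ on active) among n at risk (n₁ on active):

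U = Σ (D₁ − D·n₁/n), V = Σ D·(n₁/n)(1 − n₁/n)(n − D)/(n − 1), Z = U/√V, reject if |Z| > 1.96.

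The sums run over weeks in one pool (unstratified), or over weeks within the four cells (stratified), on the same simulated data.

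**First simulation.** Assumed: permuted blocks of 6 within strata, 35% severe, 20% North America with region not prognostic, exponential times, 15% competing events by Week 16 with equal hazard in both arms. There were 60,000 runs for size (SE √(0.05 × 0.95/60,000) = 0.09 points) and 30,000 for power (SE at most √(0.25/30,000) = 0.29 points per test). All 450 subjects; gains are in percentage points.

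| Severe-to-moderate event-rate ratio | 0.80 | 0.70 | 0.50 | 0.33 | 0.20 |
|---|---|---|---|---|---|
| 20% vehicle incidence: unstratified size, % | 5.1 | 4.9 | 4.9 | 4.5 | 4.4 |
| Gain at hazard ratio 1.4 | 0.1 | 0.3 | 0.8 | 1.8 | 2.9 |
| Gain at hazard ratio 1.8 | 0.1 | 0.3 | 0.7 | 1.7 | 3.0 |
| 25% vehicle incidence: unstratified size, % | 5.0 | 5.0 | 4.7 | 4.5 | 4.1 |
| Gain at hazard ratio 1.4 | 0.0 | 0.3 | 1.1 | 2.6 | 4.1 |
| Gain at hazard ratio 1.8 | 0.1 | 0.2 | 0.7 | 1.6 | 3.0 |
| Unadjusted Cox limit when the conditional hazard ratio is 1.8 (20% incidence) | 1.80 | 1.80 | 1.79 | 1.77 | 1.75 |

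- Stratified size at 20% incidence is 4.9–5.1%. At hazard ratio 2.2 the gain is 0–0.7.
- Reversed prognosis (severe subjects respond 1.5 or 2.0 times as often), 20–25% incidence: size 5.0% and 4.7–4.8%; gain at hazard ratio 1.4 of 0.4 and 1.2–1.5.
- Random 60% subset (0.60 × 450 = 270), 20–25% incidence: gain at most 1.1 at ratios of 0.50 or milder, 1.2–2.5 at 0.33, 2.1–4.8 at 0.20.
- Strata not prognostic: change of 0.1 or less in all 450; loss of 0–0.4 in the subset.

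**Second simulation, different assumptions.** 30% severe, 15% North America, vehicle event risk 25% before competing events (weekly hazard −ln(0.75)/16 = 0.0180), intercurrent-event risk 20% on vehicle and half that hazard on active, hazard ratio 1.6, 6,000 runs. Both factors were varied.

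| Severe / region hazard ratio | Gray, unstratified → stratified, % | Cause-specific, unstratified → stratified, % |
|---|---|---|
| 1 / 1 | 78.47 → 78.53 | 69.17 → 68.97 |
| 0.7 / 0.9 | 73.75 → 74.18 | 63.40 → 63.95 |
| 0.5 / 0.8 | 69.95 → 70.82 | 58.88 → 60.62 |
| 0.33 / 0.7 | 65.55 → 67.03 | 54.67 → 57.45 |

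The gains are therefore 0.1 to 1.5 points for Gray's test and −0.2 to 2.8 for the cause-specific (Cox score) test. Type I error with equal intercurrent-event hazards was 4.1–5.2% unstratified and 4.4–5.3% stratified. At about 20% vs 40% (hazard ratio ln(0.60)/ln(0.80) = 2.29), Gray's test stays at 98.7% and the cause-specific test moves from 96.8% to 97.2%.

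**Repeat of the first setting** (20% incidence, hazard ratio 1.4): gains of 0.9, 1.9 and 3.0 points at ratios 0.50, 0.33 and 0.20, and 0 to 0.3 points lost if the strata are not prognostic.

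**The case against.** The strongest reply is that nothing here is an error. The unstratified tests are valid, the endpoints are exploratory, and the text is silent on strata; it does not rule them out. The estimand is marginal: the probability of responding before an intercurrent event or Week 16. An unstratified Gray's test with curves by arm matches it directly, whereas a stratified test and conditional hazard ratios sit less neatly beside marginal curves. Where stratified CMH is used, the summary is stratified too.

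The benefit also depends on assumptions. At 20% incidence and ratios of 0.50 or milder the gain is at most 0.8 points, and a size of 4.9–5.1% with a simulation error of 0.09 shows no clear conservatism. Ratios of 0.33 and 0.20 have no support in the protocol. Treating the subsets as random ignores that they are selected on baseline symptom score, and equal competing risks are doubtful because Section 5.3 links most intercurrent events to lack of efficacy or unacceptable treatment features.

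Most of this stands and limits the size of the point. It does not remove it. Halving the intercurrent-event hazard on active (second simulation) leaves the same picture. The mismatch of targets is handled by keeping the marginal curves and labelling the hazard ratio. The cost when the strata are irrelevant is a few tenths of a point, so the change is nearly free in power and not strictly free. The protocol itself gives prognosis as its reason for stratifying on IGA-CHE.

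**Conclusion.** The omission is real and the concern holds as a minor improvement. Under moderate assumed prognosis (ratio 0.50 or milder), stratifying gains about 1 point or less for Gray's test. In the second simulation, the cause-specific test gains up to 1.7 points at severe and region hazard ratios of 0.5 and 0.8. Stronger assumed prognosis (ratios 0.33 to 0.20) gives Gray's test roughly 1.5 to 4 points in all 450 subjects at hazard ratios of 1.4 to 1.8; gains shrink when the treatment effect is large. If the strata are not prognostic, the cost is at most about 0.4 points. The hazard ratio itself hardly moves (1.80 to at worst 1.75 at 20% incidence).

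Confidence is high in the omission and the remedy. The size rests on assumptions for prognostic strength, severe fraction, competing risk, hazard ratio and subset size, none of which the protocol gives for these endpoints. Type I error is not inflated and no confirmatory result changes.

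**What to change.** In Section 14.3.6.4, or in the SAP that Section 14.3.14 says will be finalised while the data are still blinded, specify that Gray's test and the cause-specific Cox models are stratified by region and baseline IGA-CHE score. Keep the Aalen-Johansen curves by treatment group, and their differences at Weeks 2, 4 and 8, as the marginal effect summary. State that the stratified hazard ratio is conditional on stratum.

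The cost is one sentence and a strata option in standard software. Sample size, data collection, timelines and the confirmatory tests are unaffected.

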# 14.3.7 Analysis of primary endpoint

The primary endpoint will be analysed as described in Sections 14.3.6.1 and 14.3.6.2. The confirmatory one-sided (superiority) hypothesis, described in Section 14.3.5, will be tested for delgocitinib cream 20 mg/g vs. cream vehicle based on the primary analysis for the primary estimand.

# 14.3.8 Analysis of key secondary endpoints

The confirmatory hypotheses for key secondary endpoints, presented in Sections 14.3.6.1 and 14.3.5, will be tested based on the primary analyses for the primary estimand strategies described in Sections 14.3.6.2 and 14.3.6.3.

Panel 24 provides an overview of the primary analysis of the key secondary endpoints related to the primary and supplementary estimands. For further details, including sensitivity analysis, refer to Section 14.3.6.

Page 118 of 157

Panel 24: Overview of the primary analysis of the key secondary endpoints related to the primary and supplementary estimands

		Primary estimand		First supplementary estimand		Second supplementary estimand	
Key secondary endpoint	Type of endpoint	Strategy to handle IEs	Handling of missing data and data collected after IE	Strategy to handle IEs	Handling of missing data and data collected after IE	Strategy to handle IEs	Handling of missing data and data collected after IE
Reduction of HESD itch score (weekly average) of ≥4 points from baseline at Week 16  Reduction of HESD score (weekly average) of ≥4 points from baseline at Week 16 	Binary	Composite	Non-response imputation	Pandemic modified composite	Independent of the COVID-19 pandemic: non-response imputation Related to the COVID-19 pandemic: MI assuming MAR within treatment group	Treatment policy	Independent of the COVID-19 pandemic: MI assuming MAR within treatment group and occurrence of IEs  Related to the COVID-19 pandemic: MI assuming MAR within treatment group
IGA-CHE TS at Week 8 IGA-CHE TS at Week 4	Binary	Composite	Non-response imputation	Pandemic modified composite	Independent of the COVID-19 pandemic: non-response imputation  Related to the COVID-19 pandemic: MI assuming MAR within treatment group	Not applicable	Not applicable

 Trial ID: LP0133-1402
 Date: 20-Aug-2021
 Version: 4.0, Final

 Page 119 of 157
 Page 119 of 157

·		Primary	estimand	First supplementary estimand		Second supp	lementary estimand
Key secondary endpoint	Type of endpoint	Strategy to handle IEs	Handling of missing data and data collected after IE	Strategy to handle IEs	Handling of missing data and data collected after IE	Strategy to handle IEs	Handling of missing data and data collected after IE
Reduction of HESD itch score (weekly average) of ≥4 points from baseline at Week 8¹  Reduction of HESD itch score (weekly average) of ≥4 points from baseline at Week 4¹  Reduction of HESD itch score (weekly average) of ≥4 points from baseline at Week 2¹  Reduction of HESD score (weekly average) of ≥4 points from baseline at Week 8²  Reduction of HESD score (weekly average) of ≥4 points from baseline at Week 8²  Reduction of HESD score (weekly average) of ≥4 points from baseline at Week 4²	Binary	Composite	Non-response imputation	Pandemic modified composite	Independent of the COVID-19 pandemic: non-response imputation  Related to the COVID-19 pandemic: MI assuming MAR within treatment group	Not applicable	Not applicable

Page 120 of 157

		Primar	y estimand	First supp	First supplementary estimand		lementary estimand
Key secondary endpoint	Type of endpoint	Strategy to handle IEs	Handling of missing data and data collected after IE	Strategy to handle IEs	Handling of missing data and data collected after IE	Strategy to handle IEs	Handling of missing data and data collected after IE
Reduction of HESD pain score (weekly average) of ≥4 points from baseline at Week 16 	Binary	Composite	Non-response imputation	Pandemic modified composite	Independent of the COVID-19 pandemic: non-response imputation  Related to the COVID-19 pandemic: MI assuming MAR within treatment group	Treatment policy	Independent of the COVID-19 pandemic: MI assuming MAR within treatment group and occurrence of IEs  Related to the COVID-19 pandemic: MI assuming MAR within treatment group
Reduction of HESD pain score (weekly average) of ≥4 points from baseline at Week 8³ Reduction of HESD pain score (weekly average) of ≥4 points from baseline at Week 4³	Binary	Composite	Non-response imputation	Pandemic modified composite	Independent of the COVID-19 pandemic: non-response imputation  Related to the COVID-19 pandemic: MI assuming MAR within treatment group	Not applicable	Not applicable

 Trial ID: LP0133-1402
 Date: 20-Aug-2021
 Version: 4.0, Final

 Page 121 of 157

		Primary estimand		First supplementary estimand		Second supp	lementary estimand
Key secondary endpoint	Type of endpoint	Strategy to handle IEs	Handling of missing data and data collected after IE	Strategy to handle IEs	Handling of missing data and data collected after IE	Strategy to handle IEs	Handling of missing data and data collected after IE
HECSI-90 at Week 16 HECSI-75 at Week 16	Binary	Composite	Non-response imputation	Pandemic modified composite	Independent of the COVID-19 pandemic: non-response imputation  Related to the COVID-19 pandemic: MI assuming MAR within treatment group	Treatment policy	Independent of the COVID-19 pandemic: MI assuming MAR within treatment group and occurrence of IEs  Related to the COVID-19 pandemic: MI assuming MAR within treatment group
HECSI-75 at Week 8	Binary	Composite	Non-response imputation	Pandemic modified composite	Independent of the COVID-19 pandemic: non-response imputation  Related to the COVID-19 pandemic: MI assuming MAR within treatment group	Not applicable	Not applicable

Page 122 of 157

		Primary	estimand	First suppl	lementary estimand	Second supp	lementary estimand
Key secondary endpoint	Type of endpoint	Strategy to handle IEs	Handling of missing data and data collected after IE	Strategy to handle IEs	Handling of missing data and data collected after IE	Strategy to handle IEs	Handling of missing data and data collected after IE
Percentage change in HECSI score from baseline to Week 16 Change in DLQI score from baseline to Week 16 Change in HESD score (weekly average) from baseline to Week 16 Change in HESD itch score (weekly average) from baseline to Week 16 Change in HESD pain score (weekly average) from baseline to Week 16 Week 16	Continuous	Composite	WOCF (including baseline value)	Pandemic modified composite	Independent of the COVID-19 pandemic: WOCF (including baseline value)  Related to the COVID-19 pandemic: MI assuming MAR within treatment group	Treatment policy	Independent of the COVID-19 pandemic: MI assuming MAR within treatment group and occurrence of IEs  Related to the COVID-19 pandemic: MI assuming MAR within treatment group
Change in HEIS score from baseline to Week 16 Change in HEIS PDAL score from baseline to Week 16	Continuous	Composite	WOCF (including baseline value)	Pandemic modified composite	Independent of the COVID 19 pandemic: WOCF (including baseline value)  Related to the COVID 19 pandemic: MI assuming MAR within treatment group	Not applicable	Not applicable

		Primary estimand		First supplementary estimand		Second supplementary estimand	
Key secondary endpoint	Type of endpoint	Strategy to handle IEs	Handling of missing data and data collected after IE	Strategy to handle IEs	Handling of missing data and data collected after IE	Strategy to handle IEs	Handling of missing data and data collected after IE
Reduction of DLQI score of ≥4 points from baseline at Week 16 	Binary	Composite	Non-response imputation	Pandemic modified composite	Independent of the COVID-19 pandemic: non-response imputation  Related to the COVID-19 pandemic: MI assuming MAR within treatment group	Treatment policy	Independent of the COVID-19 pandemic: MI assuming MAR within treatment group and occurrence of IEs  Related to the COVID-19 pandemic: MI assuming MAR within treatment group

- 1) Among subjects with a baseline HESD itch score (weekly average) ≥4 points.
- 2) Among subjects with a baseline HESD score (weekly average) of ≥4 points.
- 3) Among subjects with a baseline HESD pain score (weekly average) of  $\geq 4$  points.
- 4) Among subjects with a baseline DLQI score of ≥4 points.

Abbreviations: COVID-19 = coronavirus disease 2019; DLQI = Dermatology Life Quality Index; HECSI = Hand Eczema Severity Index; HECSI-75 = at least 75% improvement in HECSI from baseline; HECSI-90 = at least 90% improvement in HECSI from baseline; HESD = Hand Eczema Symptom Diary; HEIS = Hand Eczema Impact Scale; IE = intercurrent event; IGA-CHE = Investigator's Global Assessment for chronic hand eczema; IGA-CHE TS = IGA-CHE treatment success, i.e. an IGA-CHE score of 0 (clear) or 1 (almost clear) with a ≥2 step improvement from baseline; IMP = investigational medicinal product; MAR = missing at random; MI = multiple imputation; PDAL = Proximal Daily Activity Limitations; WOCF = worst observation carried forward.

Page 124 of 157

